## 8. Study procedures:

Procedure/Activity	Frequency
Patient randomization	Randomization will occur in clusters of one week. All patients in the same week will receive the same therapy (ketamine or placebo), with the choice being determined by a pre-generated random sequence.
intraoperative ketamine bolus (0.5mg/kg) vs placebo followed by continuous infusion 5 mcg/kg/min	once
postoperative ketamine infusion (2.5 mcg/kg/min, up to 100kg max) vs placebo for 48 hours	once
electronic medical record chart review	for data capture and statistical review

Data will be abstracted from the EMR. Some data will be obtained through the Research Derivative. The Research Derivative is a database of clinical and related data derived from the Medical Center's clinical systems and restructured for research. Data is repurposed from VU's enterprise data warehouse, which includes data from StarPanel, VPIMS, and ORMIS (Operating Room Management Information System), EPIC, Medipac, and HEO among others. The medical record number and other person identifiers are preserved within the database. Data types include reimbursement codes, clinical notes and documentation, nursing records, medication data, laboratory data, encounter and visit data, among others. Output may include structured data points, such as ICD 9 codes or encounter dates, semi-structured data such as laboratory tests and results, or unstructured data such as physician progress reports. The database is maintained by the Office of Research Informatics under the direction of [name].

**Due to a national shortage of ketamine, study enrollment was paused on April 3rd, 2023 and then resumed on September 18th, 2023.**

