To better understand the potential efficacy of ketamine, a per protocol cohort will be analyzed which will include patients in both arms who did not have the study infusion stopped for adverse effects. The per-protocol cohort includes participants who finished the 48-hour post-operative infusion (either ketamine or placebo), as well as participants for whom the study infusion was intentionally discontinued early because the patient met appropriate recovery milestones and was preparing for discharge. However, this per-protocol cohort will exclude any patients in whom the study infusion was stopped for intolerance or side effects, including those patients who were discharged prior to 48 hours but had the post-operative study infusion stopped prior to 48 hours due to intolerances or side effects.

Treatment Arms

Randomization of treatment arms will occur in clusters of one week so that all patients in the same week will receive the same therapy (i.e., ketamine or placebo).

- A. **Intervention:** Patients will receive a weight-based (up to 100 kg max) intraoperative ketamine bolus (0.5 mg/kg) followed by continuous infusion (5 mcg/kg/min), and an additional postoperative ketamine infusion (2.5 mcg/kg/min, up to 100 kg max) for 48 hours.
- B. **Placebo:** Patients will receive an intraoperative saline bolus followed by continuous infusion of equivalent volume to study drug dosed for 5 mcg/kg/min, and an additional postoperative saline infusion for 48 hours at an equivalent volume of infusion as the intervention arm.

Outcomes

Primary Outcome

The primary outcome is the LOS in days for the placebo arm and the intervention (ketamine) arm. LOS is defined as the time between anesthesia start and the patient being discharged (patient physically leaving the hospital).

Secondary Outcomes

1. Total consumption of post-enrollment inpatient opioids in morphine milligram equivalents during the perioperative period to hospital discharge
2. The incidence of following surgical outcomes:
 - a. rapid response team calls
 - b. transfer to ICU (not including direct transfer from OR to ICU as these patients are excluded from the study) after patient has been sent to the PACU or floor
3. The incidence of the following indications or side effects requiring early cessation of the study medication, as documented by the provider at the time of discontinuing the order (from Best Practice Advisory, BPA)
 - a. Meeting milestones/preop for discharge

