 - b. Mild side effects, but prefers discontinuation
 - c. Debilitating hallucinations
 - d. Debilitating dizziness
 - e. Hemodynamic instability
 - f. Other severe side effect

4. The incidence of ileus requiring gastric decompression as defined by orogastric or nasogastric tube placement in the postoperative period

Exploratory Outcomes

1. Instances of reoperation within the index encounter
2. VUMC hospital readmissions within 30 days post-discharge (not including ED visits)

Design Considerations

Randomization

Randomization will occur in clusters of one week. All patients in the same week will receive the same therapy (ketamine or placebo), with the selection being determined by a pre-generated random sequence.

Power and Sample Size

We anticipate the use of ketamine will reduce LOS following surgery start. To determine how long this trial will need to run to have sufficient power to detect a meaningful difference, we assumed 85% power, a type I error rate of 5%, and a 10% reduction in LOS. We estimated the within period correlation from preliminary data concerning the length of stay for major abdominal surgeries to be about 0.014. Given these assumptions, about 1514 patients would need to be included overall. An increase in sample size is necessary to accommodate for the two post-randomization exclusions that are pre-specified. We expect approximately 30 participants to be impacted by these post-randomization exclusions and will therefore increase the sample size by 30 to account for this exclusion (n=1544). Given surgical volumes, we expect 20 patients to be enrolled each week, and for the trial to last approximately 18 months.

Statistical Approach

Descriptive Analysis

We will describe the study cohort both overall and by treatment arm. To characterize the study sample, demographic and clinical data will be described. Categorical variables will be described using frequencies and proportions; continuous variables will be described using means and standard deviations as well as medians and interquartile ranges (IQR). Missingness will be recorded for each variable. To further assess the distribution of variables, graphical summaries will be displayed using graphs such as boxplots, dotplots, and/or histograms. No statistical testing will be performed to compare characteristics between groups. At a minimum, the following baseline variables will be described:

- Age (years)
- Sex assigned at birth (male, female, unknown)
- Race
 - Caucasian

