 - African American
 - American Indian
 - Asian
 - Decline to answer
 - White

- Hispanic/Latino/a
 - None of these
 - Other
 - Unknown
- Ethnicity (Hispanic/Latino, Non-Hispanic/Not Latino, Unknown)
- Weight (kg) and height (m²), and BMI (kg/m²) will be calculated with weight and height
- Van Walraven modified Elixhauser score
- History of Smoking
- Type of Surgical Procedure (colorectal, ventral hernia, or surgical oncology – mutually exclusive categories)
- Epidural vs. truncal nerve block
- Intraoperative time, as defined by anesthesia start time to anesthesia stop time
- The last American Society of Anesthesiologists (ASA) Physical Status classification associated with the surgery (anesthesia encounter)
- Opioid exposed or naïve, as defined by the perioperative medicine initial consult note
- Known history of anxiety, as defined as any code present in the patient's chart prior to, and including the date of enrollment
- Known history of depression, as defined as any code present in the patient's chart prior to, and including the date of enrollment
- Known history of PTSD, as defined as any code present in the patient's chart prior to, and including the date of enrollment

Main Analysis

The main statistical analyses will be performed with the intent-to-treat cohort. As a part of sensitivity analyses, the per-protocol analysis will be performed with the primary outcome and the first secondary outcome defined in Secondary Outcomes section (i.e., total consumption of post-enrollment inpatient opioids in morphine milligram equivalents).

Primary analysis: A mixed-effect proportional odds model will be used to compare the primary outcome (i.e., LOS) between the intervention and placebo arms with cluster as a random effect. The model will include baseline characteristics such as age, body mass index (BMI), Van Walraven modified Elixhauser score, history of smoking, epidural vs. truncal nerve block, intraoperative time, the last ASA Physical Status classification associated with the surgery, opioid naïve status, known history of anxiety, known history of depression, and known history of PTSD. Continuous variables will be modeled using cubic splines to examine non-linear relationship. For missing covariates, if the proportion of missingness is very small, single imputation will be used as appropriate; otherwise, multiple imputation will be used.

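### The primary model adjusts for intraoperative time as a baseline covariate, but it is fixed only after study drug has started, so adjustment can bias the treatment effect on length of stay

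*SAP*

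**What the plan says.** The SAP's Descriptive Analysis section opens its list with "At a minimum, the following baseline variables will be described". One entry is "Intraoperative time, as defined by anesthesia start time to anesthesia stop time".

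The primary analysis (SAP, Main Analysis) again calls its covariates baseline: "The model will include baseline characteristics such as age, body mass index (BMI), Van Walraven modified Elixhauser score". The list goes on to "epidural vs. truncal nerve block, intraoperative time, the last ASA Physical Status classification associated with the surgery". The secondary analyses reuse this covariate set.

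The outcome starts at the same moment as the covariate: "LOS is defined as the time between anesthesia start and the patient being discharged" (SAP, Primary Outcome). Study drug is given inside the covariate's interval. Protocol section 8 lists "intraoperative ketamine bolus (0.5mg/kg) vs placebo followed by continuous infusion 5 mcg/kg/min", and the SAP's Treatment Arms section agrees. Each week's arm comes from a sequence generated in advance (SAP, Randomization).

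Protocol section 12 names age, BMI, substance use and type of surgical procedure as covariates, not intraoperative time. The SAP collects procedure type and tests it as an effect modifier, but does not name it as a covariate in the primary model. Neither document justifies treating intraoperative time as baseline or plans an analysis without it.

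**The concern.** The hypothesis (protocol section 4.4; SAP Introduction) concerns the total effect of ketamine on LOS counted from anesthesia start. Conditioning on a variable that the drug can change estimates something else.

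The drug need not act on LOS through the extra minutes themselves. Long operations tend to be complex ones, so LOS is likely to rise with intraoperative time largely because of complexity. If ketamine adds some minutes, the model treats ketamine patients as though they had harder surgery and credits the drug accordingly. If it removes minutes, the error runs the other way.

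The documents make such an effect possible without showing it. Sedation is a listed side effect (protocol section 4.2), and hemodynamic instability is a listed reason for stopping the infusion (SAP, Secondary Outcomes). The baseline label adds to the problem, because a difference caused by the drug would be read as chance imbalance and taken to justify the adjustment.

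**Working it through.** **1. Order of events.** Weekly allocation → anesthesia start (both LOS and the covariate begin) → bolus and infusion → anesthesia stop (covariate fixed) → discharge (LOS ends). The covariate is therefore fixed after both randomization and first exposure.

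**2. Size on the log-LOS scale.** The plan states no figure for this point. In a linear model:

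adjusted effect = total effect − (slope of log LOS on intraoperative hours) × (drug effect on intraoperative hours)

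The identity holds whether or not the slope is causal. The only input from the documents is the 10% target reduction, |ln 0.9| = 0.105. Slopes of 0.05–0.15 per hour and shifts of 5–20 minutes are assumptions. Each cell gives the bias on log LOS and its share of 0.105:

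| Slope per hour | 5 min | 10 min | 20 min |
|---|---|---|---|
| 0.05 | 0.0042 (4%) | 0.0083 (8%) | 0.0167 (16%) |
| 0.10 | 0.0083 (8%) | 0.0167 (16%) | 0.0333 (32%) |
| 0.15 | 0.0125 (12%) | 0.0250 (24%) | 0.0500 (47%) |

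Middle case: 0.10 × 10/60 = 0.0167; 0.0167/0.105 = 16%. At zero minutes the bias is zero.

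**3. Effect on error rates.** With 85% power and 5% type I error (two-sided assumed), the implied standard error is 0.105/(1.960 + 1.036) = 0.035. Biases of 0.0042, 0.0167 and 0.0500 are then 0.12, 0.47 and 1.42 standard errors.

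- If the bias favours ketamine, type I error rises from 5% to about 5.2%, 7.6% and 30%.
- If it runs against ketamine, power falls from 85% to about 82%, 71% and 35%.

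**4. Check in the planned model type.** Proportional odds models were fitted to simulated data: one data set of 40,000 patients per scenario, LOS in whole days capped at 12, slope about 0.13 per hour, no week effect. The standard error of each log odds ratio is about 0.018.

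| True total effect | Minutes added by drug | Log OR without covariate | Log OR with covariate |
|---|---|---|---|
| None | 0 | −0.019 | −0.022 |
| None | 5 | 0.041 | −0.002 |
| None | 10 | −0.006 | −0.070 |
| None | 20 | −0.001 | −0.126 |
| 10% reduction | 0 | −0.295 | −0.307 |
| 10% reduction | 5 | −0.299 | −0.347 |
| 10% reduction | 10 | −0.299 | −0.383 |
| 10% reduction | 20 | −0.272 | −0.412 |

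When the drug adds minutes, the adjusted estimate moves towards ketamine by about 0.04–0.05 (5 minutes), 0.06–0.08 (10) and 0.13–0.14 (20). With no effect on anesthesia time, the two fits differ by about 0.01 or less.

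**5. Cost of removal.** The documents give no SD for LOS, so 1514 cannot be derived forward. Solving backwards, the design effect at 20 per week is 1 + 19 × 0.014 = 1.266, so 1514/1.266/2 = 598 per arm, and SD/mean = 0.10 × √(598/2)/2.996 = 0.577. This value gives about 380 for a 20% effect, against the stated 370. It corresponds to a log-LOS SD of √ln(1 + 0.577²) = 0.536.

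Assume that intraoperative time has an SD of 1–2 hours and a slope of 0.10 per hour. Then R² = (0.10 × SD/0.536)² = 3.5–14%. Losing that precision entirely is worth 1514 × [1/(1 − R²) − 1], or about 55–245 patients. On mean squared error, keeping the covariate wins only if the shift is below 0.035 × SD/0.536 hours, about 4–8 minutes.

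**The case against.** The strongest reply has four parts.

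- **No effect on anesthesia time is shown.** Protocol section 9 credits ketamine with cardiovascular stability, and blinding limits behavioural differences between arms. Sharing a start point with LOS does not bias anything by itself, and 20 minutes is only 0.7% of a 48-hour stay. This stands: bias requires the drug to change anesthesia time. Blinding does not rule out a pharmacological effect, however, and the bias comes mainly from the slope, not from the overlap.
- **The size rests on two assumed inputs, and 47% combines both extremes.** This is true, so the whole range should be read. Moreover, odds ratios with and without a prognostic covariate differ somewhat even when nothing is biased. The zero-minute simulations put that at about 0.01.
- **Removal costs precision.** This is a fair point. The slopes that make the bias large also make the covariate prognostic, and three procedure categories may recover only part of the loss. But keeping the variable is better only if the shift is below roughly 4–8 minutes, and the plan gives no evidence that it is.
- **The protocol's covariate list is open-ended.** So is the SAP's. The protocol's silence on intraoperative time is supporting evidence, not a contradiction.

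**Conclusion.** The concern holds. The SAP labels a variable fixed after randomization and after first exposure as baseline, and conditions both the primary and the secondary models on it. These facts can be read directly from the documents. Whether the primary estimate is materially biased is not known: it depends on whether ketamine changes anesthesia time, which the documents neither show nor exclude. Under the assumed ranges the distortion runs from negligible to nearly half of the target effect, in either direction. No size was worked out for the secondary outcomes; there the objection is that the covariate is post-treatment, and for event outcomes such as ileus it is not part of the outcome. The plan should be changed, because the primary estimate should not depend on an unverified absence of drug effect.

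**What to change.** Amend the SAP as follows:

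1. Delete intraoperative time from the primary model and from the covariates carried into the secondary models.
2. Move it out of the baseline list and report it by arm as a post-treatment variable.
3. Name type of surgical procedure as a covariate in the primary model. It is already collected and is in the protocol's model. If the operating room system holds scheduled case duration, add that as a pre-treatment marker of complexity.
4. Keep a model with intraoperative time as a labelled sensitivity analysis, read alongside the observed difference in anesthesia time between arms.

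The cost is SAP wording and possibly some precision, to the extent that procedure type and scheduled duration capture complexity less well. The sample size need not be restated, since neither document says that it relied on covariate adjustment.

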### **7. Enrollment/randomization:**

Patients presenting for elective major abdominal surgery at VUMC are automatically screened to receive care within our enhanced recovery program. Patients are approached on the day of their surgery by a physician member of our Perioperative Medicine team, who describes our goals, multimodal pathways, and obtains consent to perform a regional nerve block. Eligible patients will be consented for inclusion in the trial during this initial encounter; patients returning for a follow up procedure that meets inclusion criteria will be reapproached for consent and rerandomized as appropriate. Consent for the trial will be included as an adaptation to our current consent form for neuraxial or regional nerve block procedures, with the addition of the following language:

“Vanderbilt University Medical Center (VUMC) is a learning healthcare system where we evaluate how well our routine treatments and interventions for pain control work after surgery and possible side effects they may produce. As part of your perioperative care, you will receive a bundled approach of different pain regimens that have been shown to work both alone and together to relieve pain. At VUMC, we are studying different aspects of our routine bundled pain regimen to determine the most effective parts and combinations.

If you are eligible for enrollment in a study about treatment of your pain, you may be assigned to one of multiple routinely used regimens to help control your pain. Upon enrollment, you will be randomized to receive either a ketamine or saline infusion. We are doing this study to understand which regimens have better pain control and fewer side effects in different patients. You will have pain medicine available as you need it regardless of the regimen used. Potential side effects of those pain medicines include confusion, sleepiness, agitation, slowing of your breathing, and changes in blood pressure. Data will be collected from your medical record to evaluate how well your pain

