Adult patients presenting on a weekday for an elective major inpatient abdominal surgery at VUMC will be screened for eligibility. Indications for exclusion will be noted if they meet criteria specified in the study protocol. Two post-randomization exclusions have been prespecified for this study. First, a patient directly transferred from the operating room to the Intensive Care Unit (ICU) with an endotracheal tube placed will not be included. The rationale is that these patients are exposed to both a sedative and narcotic infusion for the duration of their intubation, which would confound the ability to determine analgesic efficacy and/or side effects from the study drug. Furthermore, Enhanced Recovery After Surgery (ERAS) protocols are not followed in the ICU, and therefore there would be significant deviations from study protocol. Importantly, we aim to study ketamine's effects within ERAS principles for specifically elective surgeries. A transfer to the ICU while intubated reflects the occurrence of a major, unintended, and unanticipated intraoperative event for these elective procedures. The focus for that patient is no longer expedited recovery, but rather life-sustaining measures. Second, abortion of planned surgical procedure will qualify as a post-randomization exclusion. These patients do not undergo the intended surgical experience, will have different care pathways and goals, and are often discharged prior to 48 hours (length of time for the intervention). This exclusion will be defined as the patient being discharged home within 23 hours of anesthesia stop time, consistent with an 'observation' status rather than 'inpatient admission' to the hospital. Manual chart review will be performed to ensure appropriate exclusion. The occurrence of these exclusions will be tracked between study arms. Eligible patients will be consented for inclusion in the trial usually on the day of their surgery; patients returning for a follow up procedure that meets inclusion criteria will be reapproached for consent and rerandomized as appropriate.

Cohort Definition for Data Analysis

Intent-to-Treat Cohort

Intent-to-treat cohort includes all participants who are eligible and did not meet exclusion criteria specified in the study protocol.

Per-Protocol Cohort

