Secondary analyses: The secondary outcomes will be analyzed with the same covariates. A mixed-effect proportional odds model will be used to evaluate difference in opioid use in the hospital between the intervention and placebo arms. For each of the binary outcomes, a mixed-effect logistic regression will be used to compare the odds of events between the two arms.

Exploratory analyses: The exploratory outcomes will be presented in tables comparing the incidences of reoperation and hospital readmission within 30 days post-discharge between two arms.

Differential Treatment Effects

Differential treatment effects will be explored by examining the interaction between the treatment indicator and each variable that potentially interacts with treatment, one variable at a time, but subgroup analysis will not be performed. The variables we consider include sex, opioid naïve status, type of surgical procedure (colorectal, ventral hernia, or surgical oncology), epidural vs. truncal nerve block, known history of depression, and known history of PTSD.

References

5. Mercadante S. Opioid Analgesics Adverse Effects: The Other Side Of The Coin. *Curr Pharm Des.* 2019;25:1-6. doi:10.2174/1381612825666190717152226.

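### Psychiatric-history covariates are cut off by calendar date, so codes entered after the first study dose on the day of surgery may count as baseline; ASA class has no stated pre-dose cut-off (minor)

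*SAP*

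**What the plan says.** The SAP's Descriptive Analysis section lists three psychiatric histories among the baseline variables. The first reads "Known history of anxiety, as defined as any code present in the patient's chart prior to, and including the date of enrollment". The entries for the other two, depression and PTSD, use the same date-inclusive window.

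The same list takes ASA class as "The last American Society of Anesthesiologists (ASA) Physical Status classification associated with the surgery (anesthesia encounter".

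On timing of enrollment, the SAP (Study Population) says "Eligible patients will be consented for inclusion in the trial usually on the day of their surgery". Protocol section 7 says "Patients are approached on the day of their surgery by a physician member of our Perioperative Medicine team" and "Eligible patients will be consented for inclusion in the trial during this initial encounter". Protocol section 8 and the SAP's Treatment Arms section place the first study dose, a bolus followed by an infusion, during the operation.

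Under Main Analysis, the SAP enters all four variables in the primary proportional odds model as baseline characteristics, and the secondary models use the covariates of the primary model. Differential Treatment Effects also names "known history of depression, and known history of PTSD" among the variables to be examined for interaction with treatment.

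**The concern.** A covariate described as baseline should be fixed before treatment can influence it. A window that closes at the end of the enrollment date stays open, for a patient enrolled on the day of surgery, through the operation and the first hours of the postoperative infusion. A diagnosis code entered in that interval could be a consequence of study drug. The trial expects such effects: hallucinations are among the side effects in protocol section 4.2 and among the SAP's reasons for stopping the infusion early.

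If ketamine produced a code and the underlying event prolonged the stay, adjusting for that code as history would remove part of the harm from the treatment effect. In a secondary model for side effects, it could treat part of a drug reaction as a prior trait. The ASA rule raises a weaker version of the question, because the last value recorded need not be the preoperative one.

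**Working it through.** The plan gives no figure on this point to reproduce. The sample size is not affected: it stays at 1514 + 30 = 1544.

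**Timing, step by step**

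1. The psychiatric window closes at the end of a calendar date (SAP, Descriptive Analysis). No clock time is given.
2. That date is usually the day of surgery (SAP, Study Population; protocol section 7). This takes the enrollment date to be the consent date.
3. The first dose is intraoperative (protocol section 8; SAP, Treatment Arms), so it normally falls on the same date, after consent.
4. For the usual patient, therefore, codes entered between the first dose and midnight are inside the window. For a patient consented on an earlier day, the window closes before the first dose.
5. No other section closes the gap. Protocol section 12 names neither the psychiatric histories nor ASA class among its example covariates, so it supplies no cut-off.
6. The ASA rule has no upper time limit within the anesthesia encounter. Nothing says that the class is, or is not, revised after dosing.

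**Size, under assumed inputs**

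The documents give no coding rates and no standard deviation for length of stay, so every input except the 10% reduction is an assumption:

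- standard deviation of log stay 0.6
- true history in 25% of patients, adding 0.1 to log stay
- a post-dose event that produces a new code and adds 0.2 to 0.5 to log stay
- the rates of new codes by arm shown in the table

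Model: log stay = noise + 0.1 × history + (0.2 or 0.5) × event + ln(0.9) × ketamine. With 4,000,000 simulated records, log stay was regressed by least squares on treatment and one covariate. The covariate was either true history alone, or true history plus the new same-day codes.

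| New codes, ketamine / placebo | Estimated reduction, pre-dose covariate | Estimated reduction, same-day codes counted | Shift (percentage points) |
|---|---|---|---|
| 0.5% / 0.5% | 9.99% | 9.99% | 0 |
| 1% / 0.5% | 9.76% to 9.90% | 9.80% to 9.93% | 0.03 to 0.04 |
| 2% / 0.5% | 9.30% to 9.72% | 9.43% to 9.83% | 0.11 to 0.13 |
| 5% / 1% | 8.17% to 9.26% | 8.57% to 9.57% | 0.31 to 0.40 |

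The pre-dose column falls below 10% because the simulated events lengthen stay more often on ketamine. That is part of the drug's total effect. The third column adjusts some of it away.

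**Hand check of the largest shift** (5% / 1%, event adds 0.5)

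- Excess of patients newly labeled with history: 0.75 × (0.05 − 0.01) = 0.03.
- Average new-label rate: 0.75 × 0.03 = 0.0225, so carriers are 0.25 + 0.0225 = 0.2725 of patients.
- Coefficient shared by all carriers: (0.25 × (0.1 + 0.5 × 0.03) + 0.0225 × 0.5) / 0.2725 = 0.0400 / 0.2725 = 0.147.
- Shift in the log effect: 0.147 × 0.03 = 0.0044, against 0.00441 simulated.
- On the percentage scale: 0.0044 × (1 − 0.0817) = 0.0040, or 0.4 percentage points.

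**The case against.** The strongest reply is that the intent is plain and the mechanism thin. The variables are called known history and sit in a baseline list. Contamination needs a diagnosis code, not just a symptom, to be entered between the first dose and midnight, and more often on ketamine. The documents describe no such coding; the SAP takes side effects that stop the infusion from the provider's entry when the order is discontinued. Patients and providers are blinded, which limits coding driven by expectation. All of this stands as a reason to expect a small effect. It does not close the window: intent is not a query rule, and blinding does not prevent a code prompted by a real drug reaction.

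Three stronger readings are tempting, and the documents do not support them.

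- **ASA class is post-treatment.** A reader might infer this from the word last. The phrase can equally be a rule for choosing among several recorded values, and no section shows a revision after dosing. Only the absence of a stated cut-off is supported.
- **The depression and PTSD interaction analyses rest on contaminated groups.** Both histories share the open window, but nothing in the documents gives a route by which a same-day dose would produce a depression or PTSD code. Anxiety, the more plausible candidate, is not an interaction variable.
- **The bias could reach 1.5%.** Multiplying an assumed coefficient of 0.3 by 5 points of excess coding gives 0.3 × 0.05 = 0.015. That treats the fitted coefficient as if new codes alone set it. True histories share the coefficient and dilute it, as the hand check shows.

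It can also be said that intraoperative time, on the same list, is measured after anesthesia start by definition. That is a separate matter and does not excuse an open window for history.

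**Conclusion.** The point holds as a minor one. On the SAP's wording, anxiety, depression and PTSD codes entered after the first dose may count as baseline for patients enrolled on the day of surgery, which is the usual case, and they then enter the primary and secondary models. For ASA class, a post-dose update is not ruled out. The documents show that contamination is permitted, not that it occurs.

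Under the assumed inputs the estimated reduction in stay moves by 0 to about 0.4 percentage points, against a planned 10%. The shift is zero when new codes are equally common in both arms, and it favors ketamine only if ketamine generates more of them. The calculation is on log stay by least squares. The planned model is proportional odds, so these figures indicate scale and are not the bias in the common odds ratio. The effect on the side-effect models was not quantified, nor was any effect through ASA class.

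**What to change.** In the SAP's Descriptive Analysis section:

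- Define history of anxiety, depression and PTSD by codes time-stamped before anesthesia start, or dated before the day of surgery where no time stamp exists.
- State that diagnoses first assigned after anesthesia start in the index admission do not count.
- Define ASA class as the last one recorded before anesthesia start.

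The cost is a few words and a changed filter in the record query, with no change to sample size or conduct. The downside is that a few true histories first coded on the day of surgery may be missed where no time stamp exists.
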